Study Protocol with Statistical Analysis Plan

Study Title: Persisting Effects of Psilocybin

Clinical Trials ID (NCT number): NCT02971605

Last Protocol Approval Date: April 24, 2017

This open-label, non-blinded study will involve 12 volunteers who will receive a high dose of psilocybin under supportive conditions. Assessments (questionnaires and emotional tasks) will be conducted during screening sessions, and 1 day before, 1 week after, and 1 month after the high-dose psilocybin session. Functional magnetic resonance imaging (fMRI) will also be conducted 1 day before, 1 week after, and 1 month after the psilocybin session.

Primary objectives:

1. Assess the effects of psilocybin on the neural circuitry of emotion processing as measured by functional magnetic resonance imaging (fMRI) at 1 week and 1 month timepoints after psilocybin administration

Secondary objectives:

1. Assess the effects of psilocybin on emotional processing at 1 week and 1 month timepoints after psilocybin administration, well after acute subjective effects of the drug have subsided
2. Assess the effects of psilocybin on personality at 1 week and 1 month timepoints after psilocybin administration

Inclusion/Exclusion Criteria

Overview of Screening Procedures: Participants will be screened via telephone to determine whether they meet major inclusion/exclusion criteria, and thus whether they are eligible for an in-person screening session. Participants who do not fail telephone screening will be invited to BPRU on the Johns Hopkins Bayview Campus for in-person screening.

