Consent will be obtained at the BPRU at a scheduled meeting after participants have passed telephone screening. Participants will be allowed to take as much time as necessary to decide whether or not to sign consent. Study staff will discuss the consent form with the participant after the participant has read the consent form. Study staff will ask questions to assess the individual's understanding of the consent form. Participants may take the consent form home to review and return to sign consent if they wish. Participants who might be eligible for a future study will be asked to complete IRB-approved HIPAA-IRB Form 3 "Authorization to contact you about future research studies". Participants' files will be kept in a locked room and treated as confidential research material. All data will be collected using the unique identification code numbers assigned to each participant upon entry to the study. No individual identifiable information will be released without written authorization. These procedures have been used in the past to protect confidentiality of study data and no instance of loss of confidential information has occurred.

Participants will be physically and psychologically healthy adult participants (approximately equal numbers of males and females) 18 to 45 years old. Non-English speakers and those with language or hearing impairments will not participate in the study. Participants will be recruited primarily from the Baltimore/Washington DC metro area. Participants will have used hallucinogens in the past, although preference will be given to those who have had minimal prior use (e.g. 1 to 2 prior uses) that was at least 3 months ago. Potential participants will be carefully screened to eliminate those with significant medical or psychiatric illnesses (see below for specific inclusion/exclusion criteria).

We expect to consent up to 100 volunteers at Johns Hopkins (some of whom will not pass the in-person screening), in order to achieve 12 participants who provide complete data.

Screening evaluation will include a history and physical examination, ECG, a 30 cc blood draw for medical screening (e.g., complete blood count and Quest Test 18T Comprehensive metabolic panel with eGFR), a personal and family medical history questionnaire, psychiatric interview (SCID-5), and a urine drug test.

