Longitudinal Emotion and Social Questionnaires: A battery of questionnaires will be completed one day before, one week after, and one month after psilocybin to assess emotional and social changes. This includes general [the Positive and Negative Affect Scale - X (Watson, Clark 1994) and the Profile of Mood States (McNair, Lorr & Droppleman 1992)] and emotion-specific [the Dispositional Positive Emotions Scale (Shiota, Keltner & John 2006), the Depression Anxiety Stress Scale (Lovibond, Lovibond 1995), and the State Trait Anxiety Inventory (Spielberger et al. 1983)] measures, as well as a measure of social cognition [the Social Value Orientation test (Murphy, Ackermann, & Handgraaf, 2011)]. Outcome measures will consist of the validated scale scores for each questionnaire.

Longitudinal and Follow-Up Questionnaires: Participants will complete the Big Five Inventory (BFI) (John, Naumann & Soto 2008) , the Brief Affective Neuroscience Personality Scales (BANPS) (Barrett, Robins & Janata 2013) , the Tellegen Absorption Scale (Tellegen, Atkinson 1974) , and the Emotion Regulation Questionnaire (Gross, John 2003) which are validated measures of personality traits. These questionnaires will be administered during screening and at the 1-month post-psilocybin imaging session, in order to test the hypothesis that openness and positive emotional personality traits will increase, and negative emotional personality traits will decrease, after psilocybin administration. A prior study in our laboratory found changes in the domain of openness following psilocybin (MacLean, Johnson & Griffiths 2011) .

Statistical plan

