Assessing the effects of psilocybin on emotional processing. We hypothesize that psilocybin administration will lead to impaired recognition of negative emotional facial expressions, decreased emotional conflict to incongruent emotional stimuli during an emotional conflict processing task, decreased negative affect, and increased positive affect one week and one month after psilocybin administration, relative to baseline. Outcome measures of the emotion recognition task and emotional conflict Stroop task will be separately submitted to two-way repeated measures ANOVA, with assessment time-point (baseline, one week and one month post-psilocybin) and emotional valence of stimuli (positive vs negative) as within-subject factors. F-tests will be used to assess whether there is a main effect of assessment time point and an effect of the interaction between assessment time point and emotional valence on each outcome measure. Planned comparisons will be used to test the hypothesis of impaired responding to negative emotional stimuli (confirmed by finding increased reaction time and decreased accuracy), and facilitated responding to positive emotional stimuli (confirmed by finding decreased reaction time and increased accuracy) at each post-psilocybin time point (one week, one month) compared to baseline. Outcome measures of the longitudinal questionnaires will be separately submitted to a one-way repeated measures ANOVA, with assessment time-point as a within-subject factor. An F-test will be used to assess whether there is a main effect of assessment time point on each outcome measure.

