Assessing the effects of psilocybin on the neural circuitry of emotion processing. We hypothesize that psilocybin administration will reduce amygdala BOLD response to negative emotional stimuli during emotion recognition and discrimination tasks, and ACC BOLD response during emotional conflict processing, one week and one month post-psilocybin. Whole-brain BOLD EPI data will undergo standard preprocessing (realignment/motion correction, co-registration across runs, normalization to the MNI template, smoothing, motion censoring or “scrubbing” (Power et al. 2012) , physiological artifact correction (Behzadi et al. 2007) , 36-parameter confound regression and spike regression (Satterthwaite et al. 2013)). Regions of interest (ROI) analysis will be performed, with ACC and amygdala as seed regions, to test the hypothesis of decreased BOLD response to negative stimuli and increased BOLD response to positive stimuli in these regions one week and one month post-psilocybin. The first eigenvector of the signal from all voxels in each region will be submitted to a mixed effects repeated measures ANOVA, with time point and the emotional valence of stimuli as within-subject main effects, and subject as a random effect. Subject-level contrasts will assess effects of task condition at each time point. Second-level t-tests will be used for planned comparisons to test the hypothesis of lower BOLD response to negative stimuli and higher BOLD response to positive stimuli post-psilocybin. We will repeat these analyses as whole-brain voxel-wise analyses to evaluate change outside of hypothesized regions. Preprocessing and whole-brain statistical analysis will be conducted using Statistical Parametric Mapping (SPM; <http://www.fil.ion.ucl.ac.uk/spm/software/spm12/>) in MATLAB. ROI analysis will be conducted using MarsBaR (<http://marsbar.sourceforge.net/>).

Secondary Outcome Questionnaire Measures: Repeated-measures ANOVA will be used when appropriate to assess change between groups and over time within groups in secondary outcome measures. Planned

comparisons will investigate change in questionnaire test scores between pre-session and post-session timepoints.

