Power Analysis: Assuming a one-way ANOVA with three levels (day before, one week and one month after) and 12 subjects, we have 75.8% power to observe significant connectivity change ($p < 0.05$) for a small observed effect size ($r=0.25$). The proposed study will provide data to directly estimate the effect of psilocybin on longer-term change in emotion and neural circuitry.

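### The three-time-point F-tests and the ROI BOLD model specify no sphericity correction, covariance structure or error terms, so their 5% level rests on unstated assumptions

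*Combined protocol and SAP*

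**What the plan says.** The Statistical plan has three families of test with time as a three-level factor.

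- **Task outcomes** (paragraph on emotional processing): accuracy, response time and the other outcomes of the recognition and Stroop tasks are "separately submitted to two-way repeated measures ANOVA, with assessment time-point" and valence as within-subject factors. F-tests cover time and time by valence.
- **Emotion and social questionnaires** (same paragraph): "Outcome measures of the longitudinal questionnaires will be separately submitted to a one-way repeated measures ANOVA, with assessment time-point as a within-subject factor". The test is then given: "An F-test will be used to assess whether there is a main effect of assessment time point on each outcome measure".
- **ROI BOLD** (paragraph on neural circuitry, which serves the primary objective): a mixed-effects repeated-measures ANOVA with time and valence "as within-subject main effects, and subject as a random effect".

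Scans and questionnaires share one schedule: "Functional magnetic resonance imaging (fMRI) will also be conducted 1 day before, 1 week after, and 1 month after the psilocybin session". The directional hypotheses are tested separately, by planned comparisons of each post-dose time point with baseline and, for BOLD, by second-level t-tests. The error term of the planned comparisons is not given. Sphericity, adjusted degrees of freedom and residual covariance are not mentioned anywhere, including the Power Analysis.

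**The concern.** The classical repeated-measures F-test, and a model with one random subject intercept and independent residuals, both assume that the differences between any two time points have the same variance. Dosing falls between the first and second assessments. If subjects respond differently and the response lasts, the two post-dose values will be more alike than either is to baseline. Correlation that fades with time would also break the assumption. Either way, the F-test can reject a true null more often than 5%.

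The ROI model has a second weakness. Positive and negative stimuli are measured in the same scanning session. Anything that shifts a whole session for one subject moves both valences together. A model with subject as its only random term treats those two values as independent replicates of the time effect.

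At stake are the omnibus time tests, including one on the primary objective. If the correction is left open, it can also be chosen after the data are seen, across many outcomes in 12 people.

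**Working it through.** **Inputs from the documents.** Subjects: 12 ("in order to achieve 12 participants who provide complete data", screening section). Time levels: 3 ("Assuming a one-way ANOVA with three levels (day before, one week and one month after) and 12 subjects", Power Analysis). Alpha: 0.05 (Power Analysis). Variances and correlations are not given, so every covariance below is an assumption.

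**1. The plan's own figure.** The stated power is 75.8% for an effect size of 0.25. Read 0.25 as Cohen's f, with λ = f² × n × m / (1 − ρ) and 2 and 22 degrees of freedom. At ρ = 0.5, λ = 0.0625 × 36 / 0.5 = 4.5 and power is 41%. At ρ = 0.776, λ = 2.25 / 0.224 = 10.04 and power is 75.8%. So the figure is attainable only with an unstated correlation of about 0.78, and with sphericity assumed. It does not show whether a correction was intended.

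**2. Omnibus F-test over three time points.** With unit variances, the variance of a difference is 2(1 − r). Box's epsilon is ε = [tr(M)]² / (2 tr(M²)), where M is the covariance of two orthonormal time contrasts. Worked case, with correlations (baseline–1 week, baseline–1 month, 1 week–1 month) of 0.4, 0.4, 0.9:

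- difference variances: 1.2, 1.2 and 0.2;
- eigenvalues of M: 1 − 0.9 = 0.1, and (6 + 2 × (−0.8 − 0.8 + 0.9)) / 6 = 0.767;
- ε = (0.867)² / (2 × (0.588 + 0.010)) = 0.63.

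The rates below come from simulated null trials with n = 12 and the uncorrected critical value F(2, 22) = 3.44.

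| Assumed correlations | ε | Rejection at nominal 5% |
|---|---|---|
| 0.5 / 0.5 / 0.5 | 1.00 | 5.0% |
| 0.6 / 0.6 / 0.7 | 0.97 | 5.1% |
| 0.7 / 0.6 / 0.75 | 0.93 | 5.3% |
| 0.6 / 0.5 / 0.8 | 0.81 | 6.0% |
| 0.5 / 0.4 / 0.85 | 0.70 | 6.9% |
| 0.4 / 0.4 / 0.9 | 0.63 | 7.5% |
| lower bound for 3 levels | 0.50 | P(F(1, 11) > 3.44) = 9.0% |

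Correlation that decays over days −1, 7 and 30 (calendar days assumed) gives 6.0% at 0.7 per 8 days (ε 0.81) and 6.5% at 0.9 per 8 days (ε 0.74). With Greenhouse-Geisser degrees of freedom, the rows with ε of 0.81, 0.70 and 0.63 return to between 4.6% and 5.0%. The compound-symmetry row falls to about 4.2%.

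**3. ROI model with subject as the only random term.** There are 12 × 3 × 2 = 72 values. After 12 subject means and 5 cell contrasts, 55 residual degrees of freedom remain (if the interaction is fitted). They pool subject × time (22), subject × valence (11) and subject × time × valence (22). Let σ²ₛ be the variance shared by both valences in one session and σ²ₑ the rest. Then:

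- expected mean square for time under the null: σ²ₑ + 2σ²ₛ;
- expected pooled error: [22(σ²ₑ + 2σ²ₛ) + 33σ²ₑ] / 55 = σ²ₑ + 0.8σ²ₛ.

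Assume that subjects account for 50% of total variance:

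| Shared within session | Time | Pooled error | Ratio | Rejection at nominal 5% |
|---|---|---|---|---|
| 0% | 0.50 | 0.50 | 1.00 | about 5% |
| 10% | 0.60 | 0.48 | 1.25 | about 9% |
| 25% | 0.75 | 0.45 | 1.67 | about 16% |

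These rows have no sphericity violation, so this problem is separate from step 2. Testing time against subject × time restores 5%. The interaction errs the other way: at 10% shared its expected mean square is 0.40 against 0.48, so the pooled test is conservative.

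**4. Planned comparisons.** One week against baseline, tested with its own error (11 degrees of freedom), rejects 4.9% to 5.1% throughout. Tested with the ANOVA's pooled error (22 degrees of freedom), it rejects about 6%, 8% and 10% at ε = 0.81, 0.70 and 0.63. Pooling need not inflate: with 0.7 / 0.6 / 0.75 this difference has variance 0.6 against an average of (0.6 + 0.8 + 0.5) / 3 = 0.63.

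**The case against.** A reader might infer that the plan prescribes uncorrected tests, and that every time effect is therefore inflated. The documents do not support that. They are silent, and an analyst could apply a correction without departing from the text. Nor does the ROI paragraph rule out a richer residual covariance.

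A reader might also blame the unequal spacing of the visits. Spacing alone does not break sphericity: compound symmetry gives 5.0% whatever the gaps. The two mechanisms also partly offset each other. Decay over gaps of about 8 and 23 days makes baseline and one week the most alike pair, whereas a lasting drug response makes the two post-dose values the most alike. Mixed patterns such as 0.7 / 0.6 / 0.75 give 5.3%. Under a true null, the dosing mechanism needs individual responses that average to zero.

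Finally, the directional hypotheses rest on single-degree-of-freedom contrasts, which need no sphericity when each uses its own error. The personality questionnaires have two occasions, so sphericity cannot fail there. The study is small and open-label, and is partly meant to provide estimates.

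All of this stands, and it limits the point to a conditional one. It does not remove it. The plan leaves the error term of the planned comparisons open, and the ROI model taken literally has one pooled error term, which spacing and offsetting correlations do nothing to repair.

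**Conclusion.** The point holds as a gap in specification with a conditional effect on type I error. For a three-time-point omnibus F-test with 12 subjects, the nominal 5% level is between 5.0% and about 7.5% under the covariances assumed here, and cannot exceed about 9%. For the ROI test of time, run with one pooled error term, it is about 9% to 16% if 10% to 25% of variance is shared within a session and subjects account for 50%; with nothing shared it is about 5%. The documents give no variances or correlations from which to choose within these ranges. Second-level t-tests and planned comparisons with their own error term, and the two-occasion personality measures, are outside the problem. This is an inexpensive improvement and not a flaw that undermines the study. The ROI error term matters most, because it bears on the primary objective and has the larger possible effect.

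**What to change.** Add to the Statistical plan:

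- All time and time-by-valence F-tests use Greenhouse-Geisser degrees of freedom and effect-specific error terms: subject by time for the time effect, and subject by time by valence for the interaction.
- If a mixed model is used instead, it has an unstructured covariance over the three time points that also allows correlation between the two valences within a session, with Kenward-Roger degrees of freedom.
- Each planned comparison uses its own error term.

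The cost is a few sentences and no new data. If sphericity does hold, the Greenhouse-Geisser test is slightly conservative at n = 12 (about 4.2% instead of 5.0%), with a correspondingly slight loss of power.

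### The plan lists confound and spike regression as preprocessing, before the task contrasts, and does not say they are fitted jointly with the task; done in that order, BOLD responses are attenuated by an amount that can differ between scans

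*Combined protocol and SAP*

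**What the plan says.** The relevant text is in the Statistical plan, under *Assessing the effects of psilocybin on the neural circuitry of emotion processing*.

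- **Preprocessing.** "Whole-brain BOLD EPI data will undergo standard preprocessing". The bracketed list that follows includes scrubbing, physiological artifact correction and "36-parameter confound regression and spike regression". It does not separate task runs from resting-state runs.
- **First level.** The contrasts come later in the paragraph: "Subject-level contrasts will assess effects of task condition at each time point". No nuisance regressors are named for this model, and nothing is said about filtering the task design.
- **Group model for the regions of interest.** The terms are "time point and the emotional valence of stimuli as within-subject main effects, and subject as a random effect". There is no motion or data-quality term.
- **Software.** "Preprocessing and whole-brain statistical analysis will be conducted using Statistical Parametric Mapping". Preprocessing and analysis are thus named as two activities.

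The plan gives no number of volumes per run, no censoring threshold and no comparison of motion across scans.

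The opening summary sets the design: "This open-label, non-blinded study will involve 12 volunteers", scanned "1 day before, 1 week after, and 1 month after the psilocybin session". There is no control group. The fMRI measures of emotion circuitry are the primary objective.

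**The concern.** The primary result is a within-person change in BOLD amplitude over three scans. It is sound only if the same true response gives the same expected estimate at each scan.

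Cleaning the data first and fitting the task afterwards does not guarantee this. Nuisance regression also removes whatever part of the task signal happens to lie along the nuisance regressors. If the task regressor is not cleaned in the same way, that part is lost from the estimate. The share lost depends on the number and timing of spikes and on how far the confounds correlate with the task, and these can vary from scan to scan.

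With one group and no motion term, the analysis could not tell a systematic scan difference in this loss from a change after dosing. More loss at the later scans would imitate the predicted fall in response to negative stimuli; less loss would hide it.

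**Working it through.** The plan has no figure of its own on this point; its power figure does not enter. The documents supply the 36 confound parameters, 12 participants, three scans and the order of steps. Run length, spike counts, autocorrelation, confound-task correlation and response variability are assumptions, chosen to show a range.

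**1. Algebra.** Let y = xβ + Zγ + e, with x the task regressor and Z the confounds and spikes, and let M remove Z.

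- Two-step (clean y, then fit x as it stands): x'My / x'x, with expectation β · x'Mx / x'x = β(1 - R²), where R² is from regressing x on Z.
- Joint fit, or x cleaned in the same way: x'My / x'Mx, with expectation β.

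This is the one-regressor form; several task conditions give the same result in matrix form.

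**2. Unrelated, uncorrelated nuisance regressors.** Here R² is about k/(T - 1), with k = 36 + spikes and T volumes.

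| Spikes | T = 150 | T = 300 |
|---|---|---|
| 5 | 1 - 41/149 = 0.725 | 1 - 41/299 = 0.863 |
| 8 | 1 - 44/149 = 0.705 | 1 - 44/299 = 0.853 |
| 20 | 1 - 56/149 = 0.624 | 1 - 56/299 = 0.813 |
| Fall, 5 to 8 | 2.8% | 1.2% |
| Fall, 5 to 20 | 13.9% | 5.8% |

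**3. Simulation, 150 or 300 volumes.** There were 36 nuisance regressors with autocorrelation 0 to 0.9, and block and event designs. With 5 spikes the two-step estimate recovered 0.20 to 0.87 of the true response. Going from 5 to 20 spikes lowered it a further 5% to 16%; going from 5 to 8 lowered it by about 0% to 6%. The joint fit recovered the true response to within a few percent (simulation error) in every setting.

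**4. Simulation, 200 volumes, block design.** Nine base signals were expanded to 36 parameters (true response 1).

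| Confound-task correlation | Spikes | Two-step | Joint |
|---|---|---|---|
| 0 | 0 | 0.64 | 1.00 |
| 0 | 10 | 0.59 | 0.98 |
| 0 | 40 | 0.48 | 0.99 |
| 0.1 | 10 | 0.55 | 1.00 |
| 0.2 | 10 | 0.42 | 0.99 |
| 0.3 | 10 | 0.29 | 1.00 |

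Going from 10 to 40 spikes gives an apparent fall of 1 - 0.480/0.593 = 19%. Going from correlation 0.1 to 0.3 gives 1 - 0.294/0.545 = 46%. Even with no spikes, 36% of the response is lost; that part is common to all scans. Multiplying the 36 confounds by five left R² at 0.577, so motion size as such does not set the factor.

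**5. Effect on a paired t-test.** With 12 participants, two-sided 0.05 and no true change, suppose R² differs systematically between two scans by d. The standardised shift is d × (mean response / SD of change).

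| d | Ratio 1 | Ratio 2 | Ratio 3 |
|---|---|---|---|
| 0.05 | 5.3% | 6.2% | 7.6% |
| 0.10 | 6.2% | 9.7% | 15.8% |
| 0.20 | 9.7% | 24.5% | 47.5% |

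Under step 2, going from 5 to 20 spikes in every participant gives d = 15/299 = 0.05 (T = 300) or 15/149 = 0.10 (T = 150). Going from 5 to 8 gives at most 3/149 = 0.02, and a false-positive rate of at most 5.4%.

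**The case against.** The strongest reply is that the plan never says the task design is left unfiltered, or that the confounds stay out of the first-level model. A preprocessing list may simply name the regressors that are later entered with the task, and then this attenuation is absent. The list also covers all BOLD data, including the 12-minute resting scan planned for connectivity work, where regression beforehand is acceptable. This stands: what is shown is a step left unspecified, whose literal order is the biased one.

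A reader might go further and infer that each scan's response is in fact shrunk according to that scan's motion, so that motion will read as a psilocybin effect. The documents do not support this. Besides leaving joint fitting open, they contain no motion data, and a loss that is equal on average across scans creates no time effect. A small shift in spike count does little.

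Nor would the artefact imitate the whole hypothesis. The plan predicts a lower response to negative stimuli and a higher one to positive stimuli; proportional shrinkage pulls both towards zero and so works against the second.

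It is also tempting to object that scrubbing and spike regression treat the same volumes twice. The plan gives neither a threshold nor an order for the two, and no harm from the overlap has been shown.

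**Conclusion.** The concern holds as a conditional one. In the listed order, with an unfiltered design, the task response is attenuated to β(1 - R²); that is algebra. Its size rests on assumed inputs: recovery of roughly 20% to 87% at 150 to 300 volumes with 5 spikes. Most of that loss would be shared by the three scans. The part that could differ is smaller under the spike shifts examined (5% to 16% for 5 to 20 spikes, about 0% to 6% for 5 to 8). It could be larger if confound-task correlation changed between scans.

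Whether any systematic difference exists, and in which direction, cannot be known from the documents. It is still worth settling beforehand, because it bears on the primary comparison and the single-group design has nothing to absorb such a difference.

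**What to change.** In the neural-circuitry paragraph of the Statistical plan:

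1. State that, for the three task runs, the confound and spike regressors are fitted in the first-level model together with the task regressors, or that the task design is residualised identically.
2. Keep regression beforehand for the resting-state connectivity data only.
3. Report mean motion and the number of censored volumes at each of the three time points.

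This removes the attenuation described here. It does not remove every way in which motion can affect BOLD data, which is why item 3 is needed as well.

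The cost is a few sentences and a pipeline setting; no new data and no burden on participants. The small downside is larger first-level standard errors, which reflect the information that the task and the nuisance regressors share. If the sponsor already fits them jointly, only the wording and the motion report change.
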